 - o If a participant has had an MRI within 6 months of screening (i.e., within 6 months from the date of informed consent) but the MRI does not follow the study-specific imaging protocol, that MRI can be used to help determine eligibility; however, another MRI must be performed per the imaging protocol, and must occur as close to, and prior to, the baseline visit, after all other eligibility criteria have been confirmed.
- Lumbar puncture*
- Post lumbar puncture safety telephone follow-up (1 to 3 days after lumbar puncture)
- Sheehan Suicidality Tracking Scale

*NOTE: Participants who have consented to participate in the CSF sub-study should undergo a lumbar puncture to obtain samples of CSF no more than 14 days prior to their first dose of study

drug at baseline. The participant's vitals should be assessed before and after the procedure, or per standard local practice. INR, PT, PTT and platelets should be assessed at the site's local laboratory at least 24 hours, and within normal range, prior to the lumbar puncture. The lumbar puncture should be done after the MRI scan if performed on the same day. If the lumbar puncture is performed on a separate day from the MRI and occurs before the MRI, then there must be at least a 3-day window between the lumbar puncture and the MRI. If the lumbar puncture is performed on a separate day from the MRI and occurs after the MRI, then there is no window (waiting period) between the MRI and lumbar puncture. Both the lumbar puncture and vMRI should occur after all other eligibility criteria have been confirmed.

Following completion of all screening assessments, results for participants who meet all inclusion and none of the exclusion criteria will be submitted via the ADCS EDC for central confirmation of eligibility. If confirmed to be eligible, permission to randomize will be issued and the participant may be randomized.

Randomization must occur at the baseline visit; otherwise, the participant will be considered a screen failure.

Re-screening

A single full re-screen (re-consent participant, assign new Participant ID and perform all screening assessments) may be conducted more than 14 days after the last assessment of a screening failure.

If the participant is failed again at re-screening, further re-screening and its minimum interval from the previous one, may be done if the PI and Central Review Medical Monitor are in agreement to do so.

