Volumetric MRI scans will use the same imaging protocol, which will include a localizer scan, a 3D T1- weighted sagittal acquisition (MPRAGE or IR-SPGR), a T2-weighted FLAIR axial acquisition, a T2* gradient recalled echo axial acquisition for magnetic susceptibility, and a diffusion weighted axial acquisition to assess for restricted diffusion.

Images will be checked for image quality and adherence to scanning protocols. 3D T1-weighted datasets passing quality checks will be corrected for spatial distortion and for intensity variation. Screening and follow-up datasets for each participant will be spatially registered to one another using rigid-body registration followed by nonlinear registration and neuroanatomic parcellation to quantify whole-brain and subregional volumetric change on a patient-by-patient basis.

The local MRI results will determine eligibility for each participant in the double blind treatment phase of the trial when the PI will confirm if MRI results are consistent with AD, meet the specified inclusion criteria, and do not have exclusionary findings as defined by the protocol. It is the responsibility of the PI to make this determination following review of the MRI, and to sign as well as date the local radiology report or the PI's own brain MRI written evaluation to acknowledge their review. The PI is at liberty to consult with a local neuroradiologist, however there is no requirement for a formal MRI read from a neuroradiologist. The ADCS Medical Safety team, or ADCS Imaging core are available to address any questions surrounding MRI eligibility. If there are safety concerns identified on this MRI, the PI should communicate with the participant's Primary Care Physician and consult with ADCS Medical Monitor, ADCS Director, and ADCS Imaging Core.

Whole brain volume (WBV, excluding cerebellum), bilateral ventricular volume and bilateral hippocampal volume will be measured. Quantitative anatomical regional change (Quarc) will be used as the computational MR image processing application. Detail for the statistical computations is given in the Statistical Analytical Plan (SAP).

If performed on the same day as a lumbar puncture, the vMRI should be conducted before the lumbar puncture. Otherwise, at least a 3-day window between vMRI and the lumbar puncture is required. Scanners that have passed the study's qualification procedures will be used. Participants must be scanned by the same scanner throughout the study.

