12.4 Analysis of Secondary Endpoints

If both the co-primary endpoints are significant, mean changes in the secondary endpoints from baseline to week 48 of the double-blind treatment phase are compared using the analysis strategy outlined above, or if appropriate, a two-sided, two-sample t-test. For these secondary endpoints, a Holm step-down test is conducted at 5% level to control the familywise error rate. These endpoints are: bilateral hippocampal volume as measured by volumetric MRI; NPI total scores; ADCS-ADL; and MMSE scores.

If the co-primary endpoints fail to both reach significance, then the secondary endpoints, will be analyzed as exploratory using the same strategy outlined above.

Categorical variables are summarized by treatment group using frequency distribution: number of non-missing observations and percentages will be given. Continuous variables are summarized using standard quantitative statistics: number of non-missing observations, mean, standard deviation, median and range (minimum and maximum observed values).

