#### 4.3.3 Adjustments for Covariates and Stratification

The analysis of the primary endpoints and other efficacy endpoints will be analyzed by comparing the change in efficacy outcome at week 48 between treatment groups using a mixed model with repeated measures (MMRM). Fixed effects in the model are APOE status (e4 carrier vs e4 noncarrier), MMSE (mild vs moderate) status, site, baseline value of the endpoint, treatment group (active vs. placebo), visit, visit x baseline and visit x treatment group interaction. Visit is treated as a categorical variable (see section 4.2.8 for definition of visit windows to be use). Subject will be included as random effects in the model. Sites with only one subject will be pooled together.

A stratified permuted block randomization procedure will be used. The stratification factors will be Screening Visit MMSE [mild: 20 to 24; moderate: 14 to 19] and Site.

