#### 4.8.3 Analysis of the Co-Primary Outcome Measures

The primary analyses use the within-participant change in ADAS-Cog 11 and in CDR-SOB as the outcome in two separate similar mixed effects repeated measures models, including all available in-clinic outcomes during the double blind phase in the mITT population. Fixed effects in the models are APOE status (e4 carrier vs e4 noncarrier), MMSE (mild vs. moderate) status, site, baseline ADAS-Cog or CDR-SOB score, respectively, treatment group (active vs placebo), visit, visit x baseline score interaction, and visit x treatment group interaction. Visit is treated as a categorical variable. Sites with only one subject will be pooled together. Descriptive statistics showing the timing of the primary outcome assessment will be presented by treatment arm as well as break-outs by baseline characteristics (e.g. APOE status, Mild/Moderate status based on MMSE, age group, and sex).

A random effect will be included for participant. The within-participant covariance will be unstructured. If the model does not converge, MMSE status will be removed from the model. If the model still does not converge, the following structures for the within-subject covariance will be fit, sequentially, until the structure is found that results in convergence of the model: Huynh-Feldt, Toeplitz, Autoregressive (1), and Compound Symmetry. Error degrees of freedom will be calculated using the Kenward-Roger approximation if an unstructured covariance is used; otherwise, a sandwich estimator will be utilized to estimate the covariance structure and degrees of freedom will be calculated using the between-within method. For the ADAS-Cog 11and CDR-SOB, each primary endpoint will be tested using model-adjusted least squares means at the week 48 visit. Point estimates, standard errors, two-sided 95% confidence intervals, and p-values will be presented.

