K=20, or in a similar manner in R. The outcome variable will be imputed in a monotone sequential manner.

- 2. Investigation of the impact of COVID-19 will be conducted by the following separate analyses:
  - i) A fixed effect to indicate an assessment occurring after March 13 (during the COVID pandemic) will be added to the model ("COVID indicator"), as well as the interaction of the COVID indicator x time. If the model with the interaction term fails to converge, the interaction term will be omitted.
  - A fixed effect to indicate the timing of the Week 48 assessment will be included in the primary analysis model. The fixed effect will be subject-based and include 2 levels. The subjects either discontinuing early or completing their in-clinic assessment within the originally specified week 48 window (Days 323-372) will be in one level of the effect and subjects with their week 48 assessment in the expanded portion of the window (days 373-420) in the another level.
  - iii) Remote assessments will be included in the model, with the model as specified for the primary analysis.
  - iv) Remote assessments will be included in the model, with the model as specified for the sensitivity analysis which includes the COVID indicator.

Additional supplemental analyses will run the primary model for each of the co-primaries but only include in-clinic "on-treatment" assessments (i.e. done within 3 days of the final dose of double-blind medication – see Section 4.3). These analysis will assess a more hypothetical estimand which focus on the effect of the study medication as intended.

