Subjects who have a baseline MRI measure and at least one MRI evaluation on-treatment following baseline will form the mITT population for this analysis. The number of images which are not quantifiable due to scan alignment failure will be summarized by study arm. The percent deformation in volumetric MRI will first be analyzed using the mITT population via an analysis of covariance (ANCOVA) with baseline MMSE as a covariate based only on subjects with an assessment in the Week 48 analysis window as the main analysis. As an exploratory analysis, an additional analysis also using the same ANCOVA model, however including all subjects with a post-baseline assessment, will be conducted to compare between BHV-4157 and placebo based on subject's last post baseline MRI.

Finally, although only the last assessed post-baseline MRI deformation will be available at time of database lock, the MRI processing team will remain blind and will process the remaining post-baseline MRIs. A subsequent analysis utilizing all on-treatment post-baseline assessments will be done based on an MMRM analysis with the model including fixed effect terms for baseline MMSE score, visit, visit x baseline MMSE score interaction, and visit x treatment group interaction. Visit is treated as a categorical variable. A random effect will be included for

participant. The within-participant covariance will be unstructured. A similar approach to calculating degrees of freedom and convergence issues will be taken as done for the primary endpoint.

As a further exploratory analysis, for Mild vs Moderate MMSE baseline status subgroups an analysis will be utilized on each subgroup using the model specification as described above.

In addition, descriptive statistics will also be presented at endpoint in the Open Label Extension Phase, by original randomized group (BHV-4157 and Placebo to BHV4157).

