#### 4.8.5.4 CSF, Serum and Plasma Biomarker Panel

CSF, serum and plasma biomarker panel (including, for example, AB42, AB42/40 ratio, total tau, p-tau-181, neurogranin, NfL, YKL-40, VILIP, SNAP-25, sTREM2, GFAP) will be assessed at screening, week 24 and week 48. CSF will be collected and analyzed in a subset of the study population (estimated n=50 active, n=50 placebo) at screening, week 24 and week 48.

The change from baseline in the response through week 48 will be analyzed using the mITT population via a Mixed Model for Repeated Measures (MMRM) analysis model, similar to the primary analysis. Fixed effects in the models are APOE status (e4 carrier vs e4 noncarrier), baseline score, treatment group (active vs placebo), visit, visit x baseline score, and visit x treatment group interaction. If appropriate, the response variable will be log transformed. Subjects who have a baseline measure and at least one evaluation on-treatment following baseline will form the study population for this analysis.

Summary statistics will be provided by arm. A p-value and 95% confidence interval for the estimated effect will be included in the summary.

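### The Holm-tested hippocampal MRI analysis adjusts only for baseline MMSE, which gives up inexpensive precision, and scan interval is not reported by arm

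*SAP*

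**What the plan says.** **Status of the test.** Protocol 12.4 lists four secondary efficacy endpoints: hippocampal volume, NPI, ADCS-ADL and MMSE. If both co-primaries succeed, "a Holm step-down test is conducted at 5% level to control the familywise error rate".

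**MRI model.** SAP 4.8.4.1 analyses percent deformation relative to the baseline scan by an "analysis of covariance (ANCOVA) with baseline MMSE as a covariate based only on subjects with an assessment in the Week 48 analysis window". The MMRM to follow, once the remaining scans are processed, also has baseline MMSE as its only baseline covariate.

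**Other models.** SAP 4.3.3 covers the primary and other efficacy endpoints and makes no exception for MRI: "Fixed effects in the model are APOE status (e4 carrier vs e4 noncarrier), MMSE (mild vs moderate) status, site, baseline value of the endpoint". ADCS-ADL and NPI follow the primary approach (SAP 4.8.4.2 and 4.8.4.3), and MMSE a similar one (4.8.4.4). The exploratory biomarker model omits site and MMSE status but keeps APOE and baseline: "Fixed effects in the models are APOE status (e4 carrier vs e4 noncarrier), baseline score, treatment group (active vs placebo", followed by visit terms.

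**Data in hand.** APOE is typed at screening. Protocol 8.7 states that "bilateral ventricular volume and bilateral hippocampal volume will be measured", and SAP 4.8.4.1 segments the baseline scan.

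**Timing.** SAP 4.3.8 Table 2 sets the Week 48 MRI window at Day 253-420. Protocol Appendix I (Table 1, footnote 11) allows a scan from 14 days before to 14 days after the visit, and asks for a scan from those terminating at week 36 or later. For the co-primaries only, SAP 4.8.3 promises that "Descriptive statistics showing the timing of the primary outcome assessment will be presented by treatment arm" and adds a sensitivity analysis: "A fixed effect to indicate the timing of the Week 48 assessment will be included in the primary analysis model".

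**On-treatment rule.** The MRI mITT needs at least one on-treatment follow-up scan. SAP 4.4 ends the on-treatment period for efficacy at the last dose plus 3 days, or at the first extension dose if that is earlier.

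**The concern.** If both co-primaries succeed, the hippocampal test is confirmatory, yet it has the shortest covariate list of the four Holm endpoints. The SAP explains why an MMRM has to wait (only the last deformation is available at database lock). It does not explain why the covariates are fewer, and the later MMRM omits them too. What is at stake is precision, not validity.

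The second issue is time. Percent deformation grows with the interval since the baseline scan, and no annualisation is stated. Scans at Day 253 and Day 420 enter the same analysis as Week 48 values. Early-termination scans from Day 253 onward fall in that window, so unequal dropout or delay could shift the mean interval by arm. An arm scanned earlier would show less atrophy for that reason alone. No planned table shows the scan interval.

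A smaller issue is that a scan taken in line with the protocol can fall outside the SAP's on-treatment period.

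**Working it through.** **1. The plan's own figures.** The documents give no power, effect size or SD for MRI. The co-primary figures reproduce: with 124 per arm, 2.64/(6 x sqrt(2/124)) = 3.46 gives 93.4% (stated 92%), and 0.95/(2.3 x sqrt(2/124)) = 3.25 gives 90.2% (stated 90%). They do not depend on the MRI model. Only the completer count is borrowed, 336 x 0.74 = 248. The MRI sample may be smaller, because scans can fail quality control or become contraindicated.

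**2. Two added covariates, without site.** Adding two terms that explain nothing to intercept, arm and MMSE multiplies the variance by about 244/242 = 1.008. If they explain a share R2, the variance factor is (1 - R2) x 1.008, and the equivalent sample is 248 divided by that factor. Power starts from an assumed 80%; 0.0125 = 0.05/4 is the first Holm step.

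| Assumed R2 | Variance factor | Equivalent n | Gain | Power at 0.05 | Power at 0.0125 |
|---|---|---|---|---|---|
| 5% | 0.958 | 259 | +11 | 81.7% | 82.0% |
| 15% | 0.857 | 289 | +41 | 85.7% | 86.6% |

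Break-even is R2 = 1 - 1/1.008, about 0.8%.

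**3. With site as well.** The documents give neither the number of sites nor the block size. Simulation with 20-50 sites, blocks of 4 within site and MMSE stratum, 26% dropout and single-subject sites pooled gives a variance factor of 1.029 to 1.115 if site explains nothing. For the whole package:
- worst case: 0.95 x 1.125 = 1.069, and 248/1.069 = 232 (-16);
- best case: 0.85 x 1.037 = 0.881, and 248/0.881 = 281 (+33).

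**4. Scan interval.**
- Analysis window alone: 420/253 = 1.66, that is 75% to 125% of 336 days.
- As scheduled, with the baseline scan 0-42 days before dosing, visit +/-7 and scan +/-14: (336+7+14+42)/(336-7-14) = 399/315 = 1.27.
- Noise as scheduled, assuming uniform timing: SD = sqrt(14^2/12 + 28^2/12 + 42^2/12) = 15.1 days. If change is linear with a 336-day mean of m SDs, v = (m x 15.1/336)^2 and the share v/(1+v) is 0.2% for m = 1 and 0.8% for m = 2.
- Bias if mean timing differs by arm, with linear change: 7/336 = 2.1% and 14/336 = 4.2% of 336-day change. In SD units a 14-day difference is m x 14/336, against a standard error of sqrt(2/124) = 0.127. For m = 1 to 2, a two-sided 5% test would have a true error rate of 6.2% to 10.1%, and a 1.25% test 1.7% to 3.4%. With balanced timing the bias is zero.

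**5. On-treatment rule against scan window.** If the last dose is on the visit day, permitted scans on days +4 to +14 are late for someone not entering the extension. For a direct entrant dosed at the visit, days +1 to +14 are late. In the main ANCOVA, an on-treatment Week 24 scan already secures entry to the MRI mITT, so only a participant without one, and with a late Week 48 scan, is affected. The later MMRM uses on-treatment scans only, so any late compliant scan is affected. The documents do not allow a count.

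**The case against.** The strongest reply is that nothing here is an error, and that stands. Protocol 12.4 allows a two-sample t-test for secondaries where appropriate, so an ANCOVA on MMSE already does more than the protocol requires. SAP 4.3.3 describes an MMRM of change; percent deformation has no baseline value of its own, and baseline volume is a substitute. The SAP varies its models by endpoint, as the biomarker panel shows. Matching 4.3.3 in full, site included, could lose precision. The 5-15% is an assumption.

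Timing is also partly covered. The co-primary timing tables reflect the visit around which the scan is scheduled, and the COVID-19 summaries in SAP 4.6 count delayed visits by treatment. Neither gives the baseline-to-follow-up interval.

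Three stronger readings are tempting:
- A reader might infer that omitting APOE or baseline volume biases the comparison. Under randomisation it does not.
- A reader might infer a much wider interval range by assuming that a scan from up to 6 months before consent can serve as the baseline scan. Protocol 8.1.1 says only of a non-conforming scan: "but the MRI does not follow the study-specific imaging protocol, that MRI can be used to help determine eligibility", with a new one then required. It does not say that a conforming earlier scan replaces the screening scan. Section 8.7 has participants scanned at screening, on qualified scanners and on the same scanner throughout. The only explicit reuse rule, for re-screening, requires the scan to be less than 3 months old at randomisation.
- A reader might infer that late compliant scans are generally lost. For the main ANCOVA they are not, as step 5 shows.

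**Conclusion.** The main MRI test is valid as written, and one main model is identifiable because the specific section governs. Two low-cost improvements and one clarification are worth making.

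The covariate gain is about 11-41 participants on an illustrative 248, against a cost of about 0.8% of precision if the terms are useless. It rests on an assumed R2 of 5-15% and on the co-primary completer count. Including site makes the direction uncertain (-16 to +33).

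Scan-interval spread is mainly a small amount of noise. It becomes bias only if timing differs by arm, at about 2.1% of linear 336-day change per 7 days. The documents do not show that it will differ, but the wide window and the early-termination scans make it possible, and one table would settle it. The on-treatment mismatch is minor and of unknown frequency.

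**What to change.** Before unblinding:

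1. **Covariates.** Add APOE e4 status and baseline hippocampal volume to the MRI ANCOVA and the later MMRM, and keep MMSE. State in SAP 4.3.3 that 4.8.4.1 governs MRI. Decide site separately: include it with small sites pooled, or record that it is left out. If included and uninformative, it costs about 3-11% of precision under the assumed 20-50 sites.
2. **Timing.** Tabulate the baseline-to-follow-up scan interval by arm. Add one sensitivity analysis using either annualised change or interval as a covariate, noting that annualising assumes linear change and that interval is partly post-randomisation. Leave the main ANCOVA unadjusted for interval. Annualising multiplies measurement error by up to 336/253 = 1.33 for the earliest scans in the window.
3. **On-treatment rule.** Reconcile SAP 4.4 and 4.8.4.1 with the protocol's +14-day scan window. State how a late compliant scan is handled, both for a participant with no on-treatment Week 24 scan and in the MMRM, and how scans shortly after a first extension dose are treated.

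The cost is SAP wording, one table and one sensitivity analysis. APOE status, baseline scans and scan dates are already collected.

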4.8.4.2 ADCS-ADL

The ADCS-ADL scale is a validated tool for assessing instrumental and basic activities of daily living based on a 23-item structured interview of the study partner. The scale has a range of 0 to 78, with lower scores indicating greater impairment.

This treatment effect will be summarized as the difference in change from baseline in the ADCS-ADL total score between the BVH-4157 and placebo groups.

The change from baseline ADCS-ADL total score will be analyzed using the mITT set via a MMRM analysis model using the same approach as in the primary analysis.

As a further exploratory analysis, for Mild vs Moderate MMSE baseline status subgroups an MMRM analysis will be utilized on each subgroup using the model specification as described above.

When computing the total score, if 25% or fewer of the questions are missing within a question category, the score for each missing question will be prorated using the average score of the completed questions, categorized by basic ADL and IADL:

Basic ADL (questions 1-6) will be prorated using the average score of completed questions 1-6 (no more than 1 of these question can be prorated).

Instrumental ADL (questions 7-23) will be prorated using the average score of completed questions 7-23 (no more than 4 of these questions can be prorated).

If more than 25% of questions with in a subgroup are missing, the total score will be missing.

The ADCS-ADL will be assessed at visits conducted in clinic or via remote communication. Only in-clinic assessments will be considered in the primary analysis; sensitivity analysis will include similar analysis including remote assessments.

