9.2.2 ADCS-Activities of Daily Living (ADCS-ADL) Scale

The ADCS-ADL scale is a questionnaire developed by the ADCS to assess functional performance in participants with AD (Galasko et al., 1997). Scores range from 0 to 75, with higher scores indicating better function.

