#### For the ADAS-Cog Total Score

The total score is the sum of 11 subscales (8 performance subtests and 3 examiner ratings). If more than two subscales (either performance subtest or examiner ratings) are missing or more than 2 performance subtests have partial missing data or if both the Word Recall and Word Recognition subtests are missing, then the ADAS-Cog total score will be missing. Otherwise, the total score will be based on the sum of the scores from the non-missing subscales multiplied (prorated) by the ratio (max ADAS-cog Total Score of 70/max total possible from non-missing subscales).

ADCS & Biohaven Pharmaceuticals Protocol BHV4157-203

For example, if the Word Recall performance subtest , which ranges from 0-10 (maximum=10), is missing, and another subtest Commands, which ranges from a score of 0-5 (maximum = 5) is also missing, then the total ADAS-cog score will be calculated as the sum from the 9 non-missing subscales multiplied by the ratio (70/(70 - (10 + 5)) = 70/55 = 1.27), the resulting prorated total score will be rounded up to the nearest integer

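### SAP 4.8.4.2 fills missing ADCS-ADL questions with a raw category mean, which is correctly scaled only if item maxima are equal within the category; on the SAP's own 0–78 range with whole-point items, at least one category cannot meet that condition

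*SAP*

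**What the plan says.** SAP 4.8.4.2 describes the ADCS-ADL as "based on a 23-item structured interview of the study partner" and adds: "The scale has a range of 0 to 78, with lower scores indicating greater impairment". Protocol 9.2.2 gives another range: "Scores range from 0 to 75, with higher scores indicating better function".

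Proration applies "if 25% or fewer of the questions are missing within a question category"; in that case "the score for each missing question will be prorated using the average score of the completed questions". There are two categories:

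- Basic (questions 1–6): missing questions "will be prorated using the average score of completed questions 1-6 (no more than 1 of these question can be prorated").
- Instrumental (questions 7–23): missing questions "will be prorated using the average score of completed questions 7-23 (no more than 4 of these questions can be prorated").

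Beyond those limits the total is set to missing. Neither document lists item maxima or says whether items score in whole points.

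Protocol 12.4 puts ADCS-ADL in the Holm family with hippocampal volume, NPI and MMSE, tested at 5% familywise only if both co-primaries are significant. SAP 4.3.4 has the same structure.

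For the ADAS-Cog total, SAP Appendix 2 handles missing subscales by a ratio of maxima: "max ADAS-cog Total Score of 70/max total possible from non-missing subscales".

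**The concern.** A raw mean of completed questions is a fair stand-in for a missing one only if they share the same maximum. If they do not, a question with a high maximum receives too few points and one with a low maximum too many, and the filled value can exceed what the question can score.

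The error matters most when the pattern of missing questions differs between baseline and week 48. It then goes into the change from baseline that is analysed, as noise or as a shift unrelated to function. The baseline total is also a covariate in the endpoint's own model and in the imputation model of the co-primary sensitivity analysis (SAP 4.8.3).

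**Working it through.** **Inputs.** From SAP 4.8.4.2: 6 basic and 17 instrumental questions, total maximum 78, proration at 25% or fewer missing. From Protocol 9.2.2: total maximum 75. Item maxima are not given.

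**Step 1: the plan's own limits.** 0.25 × 6 = 1.5, so at most 1 basic question. 0.25 × 17 = 4.25, so at most 4 instrumental questions. Both stated limits reproduce.

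**Step 2: can maxima be equal within both categories?** Let every basic question have maximum a and every instrumental question maximum b. Then 6a + 17b = 78.

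| b | 78 − 17b | a = (78 − 17b)/6 |
|---|---|---|
| 1 | 61 | 10.17 |
| 2 | 44 | 7.33 |
| 3 | 27 | 4.5 |
| 4 | 10 | 1.67 |

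No row gives a whole number, and b = 5 already exceeds 78. With whole-point items, at least one category therefore has unequal maxima. It need not be both: six basic questions at 3 leave 60 for 17 instrumental questions (mean 3.53), and 17 instrumental questions at 3 leave 27 for six basic ones (mean 4.5). If half points were allowed, a = 4.5 and b = 3 would satisfy the equation.

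For the protocol's 75, a = 4 and b = 3 works: 24 + 51 = 75. That range does not exclude equal maxima.

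**Step 3: size of the error.** Suppose a participant scores the same fraction f of the maximum on every question. Let k questions be missing, with maxima summing to M, and n be completed, with maxima summing to R. The raw-mean fill adds k × f × R/n where f × M is due, so

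error = f × (k × R/n − M).

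The assumed maxima, chosen only to be compatible with 78, are basic 6 × 3 = 18 and instrumental 9 × 4 + 8 × 3 = 60.

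| Missing instrumental questions | R / n | Error at f = 0.6 | Total at f = 1 (should be 78) |
|---|---|---|---|
| one with maximum 4 | 56/16 | 0.6 × (3.50 − 4) = −0.30 | 77.50 |
| one with maximum 3 | 57/16 | 0.6 × (3.56 − 3) = +0.34 | 78.56 |
| four with maximum 4 | 44/13 | 0.6 × (13.54 − 16) = −1.48 | 75.54 |
| four with maximum 3 | 48/13 | 0.6 × (14.77 − 12) = +1.66 | 80.77 |

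Two of the four full-function totals exceed the scale maximum. Scaling the category sum by the ratio of maxima returns 78.00 in all four cases.

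**Step 4: range over other assumed maxima.** These are extremes at full function, keeping the total at 78. With maxima of 3 to 4, one missing basic question gives an error of −1.0 to +1.0, and four missing instrumental questions −4.0 to +2.8. With maxima of 2 to 5, the ranges are −3.0 to +3.0 and −11.4 to +9.9. The outer values need the most lopsided arrangement of maxima and are bounds, not expectations.

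**Step 5: effect on the comparison.** The shift in an arm's mean total at a visit is the proportion of participants with a prorated total times their mean error. The documents give no item-missingness rate, so this cannot be evaluated.

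**The case against.** Several counter-arguments have force.

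- **Whole-point scoring is an assumption.** Neither document states it, and half points would allow equal maxima. Nothing in the documents suggests half-point items, but the inference is conditional. A reader might also infer that the range proves unequal maxima in both categories. It does not, and it cannot say which category is affected.
- **The range conflict is a separate matter.** A reader might infer that the 0–75 versus 0–78 discrepancy causes the mis-scaling. It cannot, because no maximum enters the rule. If 75 were right, equal maxima of 4 and 3 would be possible, and the raw mean would then be correctly scaled.
- **The rule matches the SAP's item-level convention.** Appendix 2 fills missing items within an ADAS-Cog subtest by the average of completed items, and Appendix 3 does the same for the neuropsychological battery. The ratio of maxima is used for whole missing subscales, whose maxima visibly differ (10 and 5 in the SAP's example). The ADCS-ADL rule is therefore not an isolated departure. But the reason for the ratio, unequal maxima, applies equally to ADCS-ADL items if their maxima differ.
- **Ratio scaling is also approximate.** It is exact only if a participant achieves the same fraction of the maximum on every question, and differing item difficulty breaks that. Its advantages are narrower: it cannot exceed the category maximum and loses nothing when maxima are equal.
- **Exposure is limited.** Proration is prespecified, capped, kept within category and identical in both arms. The endpoint is tested confirmatorily only after both co-primaries succeed.

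**Conclusion.** The point holds as a minor improvement. On the SAP's own description of 23 questions and a maximum of 78, and assuming whole-point items, the raw-mean fill is mis-scaled in at least one category. Prorated totals can then be wrong in either direction and can exceed the scale maximum.

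The size is illustrative only: about 0.3 points for one missing instrumental question and 1.5 to 1.7 points for four, with assumed maxima of 3 and 4 and 60% function. Only assessments with 1 missing basic or 1 to 4 missing instrumental questions are touched, and only where the missing questions' maxima differ from the average of the completed ones.

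A reader might go further and infer that the ADCS-ADL treatment comparison is biased. The documents do not support that: the rule is common to both arms, the sign depends on which questions are missing, and the effect on the arm difference is small if proration is rare. The differing ranges are an editorial contradiction to be settled on their own account.

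**What to change.** In SAP 4.8.4.2, replace the averaging rule by: category score = sum of completed items × (category maximum / maximum possible on completed items). Keep the limits of 1 basic and 4 instrumental questions and the rule that the total is missing beyond them. State the item maxima for the version administered so that the formula can be programmed. When maxima are equal within a category, the result is identical to the present rule.

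Separately, give the same total range in Protocol 9.2.2 and SAP 4.8.4.2 for that version.

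The cost is one SAP sentence with the item maxima and one line of scoring code, made before unblinding; the protocol range can be corrected at the next amendment. Trial conduct, sample size and the testing sequence are unaffected.
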